- The change of disability measured by the mRS, from baseline to 6 months after intervention as a continuous variable (change from baseline, so called mRS shift analysis).
- The time to intervention, defined as the period from symptom onset/last seen well to start of surgery (start surgical measures, i.e. positioning of patient) or start of medical treatment (admission of first treatment of BMT) (continuous variable, time to event).
- The temporal evolution of serum levels of the prespecified biomarkers as continuous variable from start to 6 months after intervention (continuous variable, change from baseline).
- The total time spent on the intensive care unit (ICU)/stroke unit as a continuous variable from the first admission to the ICU/stroke unit to discharge from ICU/stroke unit at 7 days/discharge after intervention (continuous variable, final value).
- The total time spent in intubation measured in minutes from the start of intubation to extubation as specified in the anesthesiology report at 7 days/discharge after intervention (continuous variable, final value).

Outcomes/Measurements applying to the intervention group only:

- The proportion of hematoma volume reduction rate (goal $\leq 15\%$ of its initial volume). The hematoma volume will be measured on serial cranial computer tomography (cCT) and the difference between the volume of the cCT used for surgery and the cCT directly after surgery will be calculated. The hematoma volume on the pre-

operative cCT will be calculated using the $(A * B * C)/2$ method during screening and secondarily validated using the volumetric function of the navigation software[34] Hematoma on directly postoperative images will be calculated using the volumetric function of the navigation software. The hematoma volume reduction rate will be a binary variable (achieved reduction < 15%/did not achieve reduction < 15%, final value).

- The relative (percentage) reduction or increase of hematoma volume from baseline admission cCT to postoperative cCT directly after surgery as a continuous variable (final value).

Additionally, we will collect baseline data of all patients such as age, sex, prior medical history and medication out of the electronic patient file.

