still intubated and sedated, patients will be transferred for a cCT in order to assess adequate hematoma evacuation. In a hybrid OR setting, the cCT will be performed directly in the operating theatre. If hematoma removal is found insufficient by the treating neurosurgeon, the patient will return to the operating theatre for further hematoma aspiration (using the same approach). After surgery patient's will be monitored and cared for in an intensive care/stroke unit. The patient will then be treated, according to the current guidelines for BMT in SSICH[12] (systolic BP <140mmHg, ICU care, controlling seizures and glucose levels).

[figure not shown]

Figure 1: Steps of the surgery: A) Planning of the access; B) Confirming the entry point; C) The burr-hole access; D) Working with the suction device and the endoscope; E) suction of hematoma; F) completely evacuated hematoma cavity

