4.3.4 V4: Day 7 assessment: 7±1 days after treatment or at hospital discharge

Clinical examination is performed as detailed for V1 except for body weight and height.

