5.1.3 Planned statistical methods

The primary analyses are performed following the intention-to-treat principle. Additionally, per-protocol analysis will be performed for sensitivity analysis. We study the ratio of positive outcomes in both study arms by performing a Bayesian A/B test after every 40 additional patients, using the method described by Gronau et al.[53]. Data collection (and the periodical analysis of these data) will continue until a Bayes Factor of 10 (or 1/10) is achieved. The odds

ratio and its 95% credible interval will be reported. Covariates ICH volume, presence of intraventricular bleeding, do-not-resuscitate orders, location of hematoma and centre will be included in a Bayesian logistic regression model

Secondary analysis is performed on the secondary outcomes. For continuous variables, a Bayesian regression with normal error term is used, for time-to-event outcomes Bayesian cox-regression is used, and for binary variables Bayesian logistic regression is used. Statistical analysis is performed with R version 4.2.1 or higher (R core Team, 2022)[54]. A complete mRS shift analysis will be calculated.

In parallel to the Bayesian primary analysis, we will perform a frequentist test of proportions comparing study arm for the first 100 patients per study arm. In the ES arm, a number of explorative analyses are performed, studying the relation between hematoma location, hematoma size, and treatment outcome. In particular, for parameters measured over time, figures are created illustrating the development over time at both the patient level and group level.

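### ICU/stroke-unit time and intubation time are defined to an end event but read out at Visit 4 as completed values, with no place for death or unfinished stays and an intubation source that probably works differently by arm

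*Protocol*

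**What the plan says.** Section 3.2 lists both durations as secondary outcomes, and the synopsis repeats the wording. Unit time runs "from the first admission to the ICU/stroke unit to discharge from ICU/stroke unit at 7 days/discharge after intervention (continuous variable, final value"). Intubation time is measured in minutes and runs "from the start of intubation to extubation as specified in the anesthesiology report at 7 days/discharge after intervention (continuous variable, final value").

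The read-out matches Visit 4, which section 4.3.4 schedules at "7±1 days after treatment or at hospital discharge". Neither place says whether the earlier or the later of the two applies.

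On analysis, section 5.1.3 states: "For continuous variables, a Bayesian regression with normal error term is used, for time-to-event outcomes Bayesian cox-regression is used". Section 3.2 labels time to intervention as time to event, but labels these two durations as continuous final values.

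Three other places bear on the intubation source:

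- Section 3.4.1 has operated patients leave theatre "still intubated and sedated, patients will be transferred for a cCT in order to assess adequate hematoma evacuation", and then go to an intensive care or stroke unit.
- Section 3.4.2 describes control care on an ICU or stroke unit, with no trial operation.
- Section 4.1 gives a rule for scoring the GCS in patients who are already intubated, so such patients can enter either arm.

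**The concern.** Three features of these definitions could distort the comparison.

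1. **Unfinished stays.** A total time to an end event cannot be a final value on day 7 for someone in whom the event has not happened. The value is either cut or undefined. If it is cut and modelled as complete, the longest stays in both arms are pulled to nearly the same number and a real difference shrinks.
2. **Early death.** A patient who dies on day 2 contributes at most about two days, less than a survivor who needs a week. Superior survival with ES is a secondary objective, so an arm that keeps patients alive could look worse on these two outcomes for that reason alone.
3. **Source.** ES patients are anaesthetised for the trial operation. Best-medical-treatment (BMT) patients are not, and may be intubated in the emergency department or ICU. A source tied to anaesthesia may capture one arm better than the other.

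What is at stake is the interpretation of two secondary resource and recovery outcomes in an open-label trial. Either result could mislead, and the direction is not predictable in advance.

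**Working it through.** The protocol gives no expected duration, standard deviation or power for these outcomes, so there is no figure to reproduce. The check first sets the text side by side, then illustrates the size.

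**Text**

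| Element | Where | Content |
|---|---|---|
| End event | 3.2 | Unit discharge; extubation |
| Read-out | 3.2, 4.3.4 | Day 7 ± 1 (days 6 to 8) or hospital discharge |
| Variable type | 3.2 | Continuous, final value |
| Model | 5.1.3 | Normal-error regression; Cox only for time-to-event outcomes |
| Intubation source | 3.2 | Anaesthesiology report only |

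For a patient past the end event at Visit 4, the rows agree. For a patient still in the unit or intubated, the first two rows cannot both be met, unless the read-out waits for hospital discharge. The third and fourth rows leave no room for censoring or for death as a competing event.

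**Illustration 1: effect of a cut at 7 days.** All inputs are assumptions: log-normal stay, log-SD s = 0.8, ES median 0.75 times the BMT median m, cap c = 7 days.

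- Mean stay = m·exp(s²/2) = 1.377·m, so the true difference = 0.25 × 1.377·m.
- Share of control stays beyond the cap = 1 − Φ((ln c − ln m)/s).
- Capped mean = m·exp(s²/2)·Φ((ln c − ln m − s²)/s) + c·[1 − Φ((ln c − ln m)/s)].

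| Control median (days) | Control stays > 7 days | True difference | Difference after cap | Retained |
|---|---|---|---|---|
| 4 | 24% | 1.4 | 0.7 | 53% |
| 7 | 50% | 2.4 | 0.6 | 27% |
| 10 | 67% | 3.4 | 0.5 | 14% |
| 14 | 81% | 4.8 | 0.3 | 7% |

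With log-SD 1.0 and medians of 5 and 7.5 days, a true difference of 4.1 days becomes 0.8.

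**Illustration 2: early death.** Assume identical survivor stays in both arms, the same cap, deaths at day 2, and mortality of 30% versus 20%. The mean recorded value is (1 − p)·c̄ + 2p, where c̄ is the capped survivor mean.

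- Median 7 days, c̄ = 5.54: 0.70 × 5.54 + 0.30 × 2 = 4.48, against 0.80 × 5.54 + 0.20 × 2 = 4.83. The difference is 0.35 day.
- Median 10 days, c̄ = 6.17: 4.92 against 5.34. The difference is 0.42 day.

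In a second set (median 5 days, log-SD 1.0, deaths uniform over days 0 to 3), early mortality of 20% versus 10% gives 4.01 versus 4.34 days, and 30% versus 10% gives 3.69 versus 4.34. In each case the arm with more early deaths has the shorter recorded time.

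**Source.** No arithmetic applies. The protocol names one source and does not describe its scope. Sections 3.4.1, 3.4.2 and 4.1 together show that intubation can begin before any trial anaesthesia, continue after theatre, or occur with no trial operation at all.

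**The case against.** **The 7-day cut is a reading, not a stated rule.** Section 3.2 does name the end events, and Visit 4 may also fall at hospital discharge. If long-stay patients were read out then, the cut would largely disappear. This stands: a reader might infer that the protocol orders truncation at day 7, and it does not say so. The visit is titled and scheduled as day 7, which makes that reading the likelier one, and the wording needs settling either way.

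**The scope of the anaesthesiology report is not described.** It is tempting to say that ventilation outside theatre is missed and that BMT values will be zero or absent. The text does not establish that. It supports only that ascertainment probably differs by arm.

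**A rule for death may sit in the statistical analysis plan.** Section 5.1.6 mentions a detailed analysis plan, which is not available here, so the absence of a rule is not itself the point. What the protocol does fix is a variable type and a model class that treat every recorded value as complete.

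**The sizes are assumed.** This is correct. The death example places 20% to 30% of patients dead at day 2. The nearest protocol figure, up to 45% at 30 days in section 2.2, is for untreated haemorrhage, and section 4.1 excludes conditions expected to compromise survival. Under the cap, deaths after day 7 cannot shorten the value, so spreading deaths over time reduces the effect.

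**The outcomes are minor.** Neither duration matches a listed secondary objective, and mortality is reported separately. That limits the importance but does not remove the defect.

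**Conclusion.** The point holds as a defect in the definition of two secondary outcomes. The end event and the read-out are not reconciled for patients still in the unit or intubated at day 7. On the likelier reading their values are cut at about 6 to 8 days and analysed as complete. On either reading, under the stated variable type and model, an early death enters as a short and favourable duration. Ascertainment of intubation time probably differs by arm, which is an inference from the care pathways rather than something the protocol states.

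The directions follow from the definitions. The sizes (7% to 53% of a true difference retained; about 0.4 day in favour of the higher-mortality arm) depend on assumed stay distributions, mortality and death times, and are not predictions for this trial. A reader should not infer that the primary result, the stopping rule or the sample size is affected; none of them uses these durations.

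**What to change.** Change the wording in both the synopsis and section 3.2:

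- Record the actual date and time of unit discharge and of extubation, from the patient record and ICU chart, in both arms. Do not rely on the anaesthesiology report alone.
- Follow each patient to the event, at the latest to Visit 6, instead of stopping at Visit 4.
- Analyse the durations so that death and unfinished stays are not completed short values, for example as time to event with death as a competing event. Section 5.1.3 should be aligned with this.

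Unit-free or ventilator-free time over a fixed window is an alternative, not a requirement. It would change the estimand by mixing in mortality, which is already a separate outcome.

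The cost is a few extra date-time fields taken from existing records and a slightly less simple analysis. Follow-up already runs to 6 months, and no trial procedure changes.

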Ethical consideration	
SSICH is a devastating disease affecting 2500 patients per year in Switzerland. As of today, nearly 60 years into the research of the ideal treatment of SSICH, effective treatment options improving not only mortality but more importantly functional outcome and HRQoL do not exist.
 
With the results of this multicenter, randomized controlled trial, we will generate highly relevant data, which will shape the future management of SSICH and lead to an improved treatment and outcome for patients.

GCP Statement	
This study will be conducted in compliance with the protocol, the current version of the Declaration of Helsinki, the ICH-GCP, the HRA as well as other locally relevant legal and regulatory requirements. A clinical trial covered by ClinO Chapter 4 may be conducted in accordance with other rules than ICH-GCP guidelines, provided that such rules are

	recognised in the specialty in question and the protection of participants and data quality and security are guaranteed (ClinO Art. 5, Abs 2).
--	--

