Baseline factors acting as confounders and/or effect modifiers potentially influencing the primary and secondary endpoints are: age, existing comorbidities and use of oral anticoagulants (OAC, including Vitamin K Antagonists [VKA], New Oral Anticoagulants [NOAC], Direct Oral Anticoagulants [DOAC]). Correction in the primary outcome analysis will be conducted for; ICH volume, presence of intraventricular haemorrhage, do-not-resuscitate orders, location of haemorrhage and centre.

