3.3 Study design

This is a national single-centre, two-arm, open labelled randomised controlled trial within the stroke units and stroke centres of the swiss stroke registry in a superiority fashion.

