3.3.3 Randomisation

Each eligible patient will be allocated to either the early ES or the BMT group in a 1:1 fashion, stratified for centre and with variable block length. This process will take place 1) after enrolment criteria were met, 2) the patient gave his/her consent or, if the patient is not able to consent, an independent physician confirmed that the interests of the patient are preserved and 3) within 24 hours after symptom onset have passed. A trained individual of the study team will implement the randomisation procedure within SecuTrial®. The allocation sequence is programmed in our CDMS SecuTrial®, which generates random block randomization algorithms

of variable length for a randomization in a 1:1 fashion. Randomisation is stratified for centre. It will also include a standard minimisation algorithm which will ensure that the treatment groups are balanced. The allocation sequence will be programmed in the CDMS by the data manager and, if necessary, a study-independent statistician. Patient ID and study arm will be generated by the randomization program and disclosed to the treating team electronically. Thus, the treatment allocation is concealed to the study team until randomization is conducted.

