4.2 Recruitment, screening and informed consent procedure

The recruitment will take place at either the emergency department or the Stroke Centre of the University Hospital Basel. Participants will be recruited by a member of the study team in the form of consecutive ongoing enrolment in daily practice as well as recruitment through a referring family physicians or peripheral hospitals to the emergency department in daily practice.

Initial screening according to the eligibility criteria pre-specified above will be performed upon admission. Some of the inclusion measurements are used in daily practice (e.g. NIHSS, GCS score evaluation, admission-imaging scan) and must be applied before informed consent is given as this is necessary to determine an underlying disease and assess study eligibility of the respective participant. These measurements serve only for the standard clinical examination used in daily emergency room practice and for testing inclusion criteria for the present study. A specific clinical examination will be performed after informed consent by the patient, a legal guardian or an independent physician was given. The investigators, a member of the study team or the attending neurosurgeon in case none of the previously named persons is available, will explain to each participant the nature of the study, its purpose, the procedures involved, the expected duration, the potential risks and benefits and any discomfort it may entail. Each participant will be informed that the participation in the study is voluntary and that the participant may withdraw from the study at any time and that withdrawal of consent will not affect the participant's subsequent medical assistance and treatment.

The participants will be informed that the participants medical records may be examined by authorised individuals other than their treating physician.

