5.1.5 Stratification for outcome analysis

Explorative stratified subgroup analysis for potential confounders (ICH volume, presence of intraventricular bleeding, do-not-resuscitate orders, location of hematoma and centre) will be conducted using Bayesian logistic regression models. An analyses of gender differences is planned.

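### The adjusted model and subgroup list use centre, which is constant if the trial has one centre, and do-not-resuscitate orders with no time limit, while age and baseline GCS/NIHSS are left out

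*Protocol*

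**What the plan says.** **Covariates.** Section 3.2 announces five variables: "Correction in the primary outcome analysis will be conducted for; ICH volume, presence of intraventricular haemorrhage, do-not-resuscitate orders, location of haemorrhage and centre". Section 5.1.3 repeats them: "Covariates ICH volume, presence of intraventricular bleeding, do-not-resuscitate orders, location of hematoma and centre will be included in a Bayesian logistic regression model". Section 5.1.5 reuses the list for "Explorative stratified subgroup analysis for potential confounders".

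**Factors named but not adjusted for.** The sentence in section 3.2 just before the correction list reads: "Baseline factors acting as confounders and/or effect modifiers potentially influencing the primary and secondary endpoints are: age, existing comorbidities and use of oral anticoagulants". None of these three is among the five covariates.

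**Number of centres.** Section 3.3 says: "This is a national single-centre, two-arm, open labelled randomised controlled trial". The objectives (synopsis and section 3.1) say the same, and section 4.2 places recruitment at one hospital: "The recruitment will take place at either the emergency department or the Stroke Centre of the University Hospital Basel". Against this, the ethical paragraph of the synopsis begins: "With the results of this multicenter, randomized controlled trial". Section 3.3 also speaks of stroke units and stroke centres of the Swiss registry, and section 6.2 of study sites in the plural.

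**Allocation.** Section 3.3.3 specifies 1:1 allocation in blocks of variable length and adds: "Randomisation is stratified for centre. It will also include a standard minimisation algorithm which will ensure that the treatment groups are balanced". It names no minimisation factors.

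**Primary test.** Sections 5.1.2.3 and 5.1.3 base the Bayes factor on a Bayesian A/B test of two proportions. Under sections 5.1.2.6 and 5.1.4, that Bayes factor decides when data collection stops.

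**The concern.** A covariate for an adjusted treatment effect should be fixed before randomisation, should vary between patients and should predict the outcome. Two of the five listed variables may fail this test.

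- **Centre** does not vary if one hospital recruits. It then contributes nothing as a covariate, defines no subgroup and stratifies nothing.
- **Do-not-resuscitate orders** have no time attached. The treating team knows the allocation, so an order written after randomisation can depend on the arm and on the early course. Adjusting for such an order, or forming subgroups on it, conditions on a possible consequence of treatment. The adjusted odds ratio then no longer estimates the total effect of allocation, and the direction of the error cannot be known in advance.

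Meanwhile age, which the protocol itself says influences the endpoints, is missing from the model. So are baseline GCS and NIHSS, which are measured anyway. At stake are the validity and the precision of the adjusted odds ratio and the subgroup results.

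**Working it through.** **1. Which analysis the covariates reach.** The plan's own figure is that about 90% of simulated trials reach a Bayes factor of 10 by 70 patients per arm (section 5.1.2.5). Inputs: control rate 0.50, risk ratio 1.6 (so 0.50 × 1.6 = 0.80 under surgery), threshold 10 or 1/10, and package default priors, assumed here to be standard normal on the mean logit and on the log odds ratio. In 1,500 simulated trials with a look every 5 patients per arm, 90.1% had reached the threshold by 70 per arm. At a single look at 70 per arm it was 86%. The stated figure is reproduced. The calculation uses only the number of good outcomes and the number of patients in each arm, so no choice of covariates changes it.

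**2. Centre.** Take a model matrix with intercept, treatment, volume, intraventricular haemorrhage, do-not-resuscitate order and location. It has 6 columns and rank 6. Adding a one-level centre column gives 7 columns and still rank 6. The new column duplicates the intercept.

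**3. Timing of do-not-resuscitate orders.** Section 3.2 places these orders outside its sentence on baseline factors. They do not appear among the V1 procedures (section 4.3.1) or in the schedule of assessments. Sections 3.3.1 and 3.3.4 confirm that care providers and patients are not blinded. Two illustrations show what a later order could do. Every input is assumed except the 50% control rate in (a).

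(a) *Effect entirely through orders.* Let 30% of control and 20% of surgical patients have an order, with 5% good outcome given an order in either arm.
- Good outcome without an order, g: 0.70 g + 0.30 × 0.05 = 0.50, so g = 0.485 / 0.70 = 0.693.
- Surgical arm: 0.80 × 0.693 + 0.20 × 0.05 = 0.564.
- Total-effect odds ratio: (0.5643 / 0.4357) / (0.50 / 0.50) = 1.295, about 1.30.
- Odds ratio within each order stratum: 1.0.

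(b) *Direct effect plus an effect through orders.* Logistic simulation with 400,000 patients, direct treatment log odds ratio 1.0 (odds ratio 2.72), log odds ratio −2.0 for an order on good outcome, and a baseline severity score affecting both.

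| Orders, control / surgery | OR adjusted for baseline severity | OR also adjusted for the order |
|---|---|---|
| 26% / 26% | 2.33 | 2.71 |
| 26% / 18% | 2.80 | 2.72 |
| 26% / 12% | 3.25 | 2.73 |
| 26% / 8% | 3.59 | 2.73 |

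The first row, where treatment does not change orders, shows that part of any difference between the columns is non-collapsibility of the odds ratio. The pattern down the columns is what matters: the severity-adjusted odds ratio rises as treatment prevents more orders, while the order-adjusted one stays at about 2.72. It cannot see the part of the effect that acts through orders.

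**4. Age, GCS and NIHSS.** Section 3.2 names age as a factor and then omits it from the correction. Section 3.3.2 promises subgroup analyses on the confounders in section 3.2, but section 5.1.5 lists only the five covariates. Section 4.2 says NIHSS and GCS are assessed before consent to establish eligibility, so pre-randomisation values exist.

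**5. Primary analysis.** Section 3.2 places the correction in the primary outcome analysis. The test in section 5.1.3 that yields the Bayes factor takes no covariates. The protocol does not say which odds ratio, adjusted or unadjusted, is the primary estimate.

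**The case against.** The strongest defence is that nothing decisive is affected. Stopping rests on the unadjusted test, and a redundant centre term drops out without biasing the treatment effect. Nowhere does the protocol say that orders placed after randomisation will be used. The other patient-level covariates can be read from admission imaging, and the time window of a covariate is often left to an analysis plan, which is not at hand here.

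Much of this stands. A reader might go further than the text allows in five ways:

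- *That the stopping decision or primary Bayes factor is biased.* It uses no covariates. For the same reason, the small number of patients at the first look is no argument here.
- *That post-randomisation adjustment is planned.* The text leaves it open. It does not commit to it.
- *That omitting age, GCS or NIHSS biases the comparison.* Under randomisation it does not. For GCS and NIHSS there is not even a contradiction, only a missed opportunity.
- *That the omission costs a definite number of patients.* The documents give no figure for explained variance. Only the increment over volume, intraventricular haemorrhage and location would count.
- *That allocation balances no prognostic factor.* Section 3.3.3 adds minimisation with unnamed factors, so this cannot be concluded.

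The defence does not remove the need to act. The protocol itself fixes the five variables, and a do-not-resuscitate order, unlike an admission scan, can arise at any time. Leaving its timing open in an open-label trial leaves open a route to bias that a few words would close. Likewise, whichever number of centres is right, some of the present text is wrong.

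**Conclusion.** The point holds for the adjusted Bayesian logistic model and the exploratory subgroups.

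- **Do-not-resuscitate orders** are the most serious part. If orders placed after randomisation are included, the adjusted odds ratio can be biased in an unknown direction. The documents support no estimate of size, because the illustrations (1.30 to 1.0, and 2.80–3.59 to about 2.72) rest on assumed inputs.
- **Centre** is uninformative if the trial is single-centre. That is the dominant statement in the protocol but not the only one.
- **Age and baseline GCS/NIHSS** are left out at the cost of some precision in the adjusted odds ratio. The age omission also sits badly with section 3.2 itself.

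The sample-size figures and the stopping rule are untouched. This is a nearly free improvement that should be made. It is not a flaw that threatens the primary Bayes factor.

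**What to change.** 1. **Sections 3.2, 5.1.3 and 5.1.5:** add age and baseline GCS or NIHSS (the screening value, taken before randomisation) to ICH volume, intraventricular haemorrhage and location.
2. **Same sections:** use do-not-resuscitate orders only if documented before randomisation; otherwise drop them from the model and the subgroups.
3. **Number of centres:** reconcile the single-centre and multicentre statements. If there is one centre, delete centre from the model, the subgroups and the stratification in section 3.3.3. If there are several, keep it and correct the design and recruitment statements.
4. **Sections 3.2 and 5.1.3:** say whether the primary estimate is the unadjusted A/B result or the covariate-adjusted odds ratio, and label the other as supportive.
5. **Sections 3.3.2 and 5.1.5:** make the promised subgroup factors agree.
6. **Section 3.3.3:** state how the blocks and the minimisation combine and on which factors. Which factor to stratify on is the sponsor's choice.

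The cost is wording and, if the centre stratum goes, one reconfiguration of the randomisation module. Age, GCS and NIHSS are already collected. Keeping do-not-resuscitate orders requires recording whether the order preceded randomisation.
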